2.5.3 Missing data

For categorical variables, patients with missing data are not included in calculations of percentages unless otherwise specified. When relevant, the number of patients with missing data is presented. Number of patients/events with imputed missing data should be identified and presented in table (if applicable).

Handling missing first IMP date and reference start date

For patient randomized and exposed with missing IMP start date the reference day will be set to randomization date.

Handling of missing weight in the calculation of basal insulin dose in (u/kg)

For calculation of basal insulin dose expressed in U/kg if the body weight measurement is missing at a given visit, the last available measurement from previous visit will be used.

Handling partial date of birth

For calculation age, missing birth day is assumed as the 15 of the month. If day and month are missing, missing birth month and day are assumed as the 15 of June. If year is missing, age could not be calculated. If calculated age is less than 18 (but not less from 17) and corresponding exclusion criteria (E02) not met, 18 will be assumed.

Handling of partial date of diagnosis of Type 2 diabetes

Partial date of diagnosis of Type 2 diabetes will be imputed to calculate the duration of diabetes.

In order to calculate:

- Duration of diabetes (year),
- Age at diagnosis of diabetes (year).

If only day is missing, only month and year will be used.

If month is missing, only year will be used in calculation.

Handling of partial date of start date of treatment with OADs

Partial start date of treatment with OADs will be imputed to calculate the OAD duration.

- If the day is missing and month is present the 15 of the month will be used.
- If year is present and equal to year of date of diagnosis of Type 2 diabetes and day and month are missing then the date of diagnosis of Type 2 diabetes will be used.
- If year is present (and not equal to year of date of diagnosis of Type 2 diabetes) and day and month are missing then the 1st July will be used.

Handling of computation of treatment duration if investigational medicinal product end of treatment date is missing

For the calculation of the treatment duration, the date of the last dose of IMP is equal to the date of last administration reported on the end-of-treatment CRF page. If this date is missing, the exposure duration should be left as missing (ie, in extent of exposure duration).

The last dose intake should be clearly identified in the CRF and should not be approximated by the last returned package date.

Handling of medication missing/partial dates

No imputation of medication start/end dates or times will be performed. If a medication date or time is missing or partially missing and it cannot be determined whether it was taken prior or concomitantly, it will be considered a prior, concomitant, and post-treatment medication.

Handling of adverse events/hypoglycemia with missing or partial date/time of onset

Missing or partial AE/hypoglycemia event onset dates and times will be imputed so that if the partial AE/hypoglycemia event onset date/time information does not indicate that the event started prior to treatment or after the TEAE/12 month on-treatment period, the event will be classified as treatment-emergent.

Furthermore, if the hypoglycemia event onset dates and times does not indicate that the event belongs:

- At time of 6-month database lock to either the 3 month on-treatment period or to the 3 to 6 month on-treatment period the hypoglycemia will be classified in both periods,
- At time of 12-month database lock to either the 6-month on-treatment period or to the 6 to 12 month on-treatment period the hypoglycemia will be classified in both periods.

These data imputations are for categorization purpose only and will not be used in listings.

No imputation is planned for date/time of AE resolution.

Handling of adverse events/hypoglycemia when date and time of first/last investigational medicinal product administration is missing

When the date and time of the first IMP administration is missing, all AEs: hypoglycemia that occurred on or after the day of randomization should be considered as treatment-emergent.

The last dose intake should be clearly identified in the CRF and should not be approximated by the last returned package date.

Handling of missing assessment of relationship of adverse events to investigational medicinal product

If the assessment of the relationship to IMP is missing, then the relationship to IMP has to be assumed and the AE considered as such in the frequency tables of possibly related AEs, but no imputation should be done at the data level.

Handling of missing severity of adverse events

If a severity is missing, estimate the missing severity/by the maximal severity/observed in the treatment arms.

Handling hypoglycemia with missing or partial time

No imputation for missing or partial time of hypoglycemia will be done.

[figure not shown]
However:

- If the minutes are missing and the hours comprised between 00 and 05, the event will be considered as nocturnal,
- If hours are missing and the patient was awakened during nocturnal, the event will be considered as nocturnal (defined by clock time).

Handling of hypoglycemia event classification when some classification items are missing

In case of information missing on the item “Assistance required”, “Associated with clinical symptoms”, or “Plasma glucose”, the following algorithm was applied:

Figure 2 - Flow chart for hypoglycemia event classification in case of missing items

As a conclusion, for cases where hypoglycemia could not be fully classified, as described above, two categories will therefore be created:

- Hypoglycemia classified as Non-classified Hypoglycemia (severity unknown) if the variable “assistance required” is equal to “missing”.
- Hypoglycemia classified as Non-classified Hypoglycemia (non-severe) if the variable “assistance required” is equal to “No”.

Handling of PRO missing data

- Handling of missing data and multiple answers on DTSQ available in user guidelines: refer to [Table 6](#).
- For Hypoglycemia Patient Questionnaire, if items 4 and 5 missing, patients will be considered as non-responders.
- For GES, if data are missing, patients will also be considered as non-responders.

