2.1.7.3 Hypoglycemia Patient Questionnaire

Patients will also complete the Hypoglycemia Patient Questionnaire, detailed in Appendix H of Achieve Control protocol (1).

This questionnaire will require them to report frequency of hypoglycemia experienced during the course of the study. Responses to Questions 4 and 5 on the Hypoglycemia Patient Questionnaire will be used to assess the endpoints. A patient report of one or more episodes of either moderate or severe hypoglycemia since the last visit will be indicative of patient experience of hypoglycemia.

The Hypoglycemia Patient Questionnaire endpoints are:

- Proportion of patients who report moderate or severe hypoglycemia since last visit on the Hypoglycemia Patient Questionnaire (Questions 4 and 5) at baseline, at 6 months and at 12 months.

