2.1.7.4 Global Effectiveness Scale

Patient and Physician reported GES: This measure, originally developed to assess the impact of treatment on asthma control, will be adapted for diabetes (GES). The GES assesses impact of treatment on a 5-point scale:

- Complete control of diabetes,
- Marked improvement of diabetes,
- Discernible, but limited improvement in diabetes,
- No appreciable change in diabetes,
- Worsening of diabetes.

These assessments will be completed twice by patients at 6 and 12 months. Physicians will complete the GES twice for each patient they manage at 6 and 12 months.

The GES endpoints are:

- Proportions of patient and provider reported “Complete control of diabetes” or “Marked improvement of diabetes” responses to GES question at 6 months and 12 months.

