2.4.7 Analyses of patient reported outcome variables

The patient report outcomes (PRO) analyses will be performed on the ITT population.

Self-reported treatment satisfaction

DTSQs and DTSQc scores at 6 and 12 months will be compared between treatment groups using an ANCOVA approach as described for the continuous efficacy variables. The ANCOVA model with satisfaction score as the dependent variable includes HbA1c target and other stratification factors used at randomization: SU use (y/n), GLP-1 RA use (y/n) and baseline HbA1c (as continuous) in the model.

The consistency between results of DTSQs change from baseline to 12 months and DTSQc scores at 12 months will be assessed.

Cumulative distribution function of score changes from baseline at 6 and 12-months will be plotted by treatment arm for each of the 3 DTSQs scores. Cumulative distribution function of 12-month DTSQc scores will be plotted by treatment arm.

Hypoglycemia Patient Questionnaire

Items of the Hypoglycemia Patient Questionnaire will be summarized by descriptive statistics. a graphical presentation will also be provided.

The proportion of patients reporting one or more episodes of either moderate or severe hypoglycemia will be compared between treatment groups using the same logistic regression model as for GES detailed in following paragraph.

Global Effectiveness Scale

At each study endpoint, the proportion of patients and providers who reported “complete control of diabetes” or “marked improvement of diabetes” at 6 and 12 months will be analyzed using a logistic regression same as the primary efficacy analysis. The dependent variable is the “complete control/marked improvement” (y/n). The logistic model includes HbA1c target and other stratification factors used at randomization: SU use (y/n), GLP-1 RA use (y/n) and baseline HbA1c (as continuous) in the model.

Additionally, at each time point (6 months and 12 months), all response choices for both patients and provider will be summarized by descriptive statistics.

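### The SAP's non-responder rule for missing hypoglycemia questionnaires is undefined for an unfavourable endpoint; read literally, it counts missing answers as no hypoglycemia

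*SAP*

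**What the plan says.** SAP 2.1.7.3 defines the questionnaire endpoint through items 4 and 5. It states that "one or more episodes of either moderate or severe hypoglycemia since the last visit will be indicative of patient experience of hypoglycemia". SAP 2.4.7 gives the analysis: "The proportion of patients reporting one or more episodes of either moderate or severe hypoglycemia will be compared between treatment groups". The model is the one specified for the Global Effectiveness Scale (GES). The population for patient-reported outcomes is ITT.

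SAP 2.5.3 then gives the missing-data rule: "For Hypoglycemia Patient Questionnaire, if items 4 and 5 missing, patients will be considered as non-responders". The next bullet deals with the GES: "For GES, if data are missing, patients will also be considered as non-responders". The GES endpoint is defined in SAP 2.1.7.4 as "Proportions of patient and provider reported “Complete control of diabetes” or “Marked improvement of diabetes” responses to GES question".

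Among the patient-reported outcomes, the SAP defines a responder only for the DTSQs (SAP 2.1.7.1), as a change from baseline of at least a minimal important difference. It gives no definition for the hypoglycemia questionnaire. The same section, SAP 2.5.3, opens with a general rule that patients with missing categorical data are left out of percentages unless something else is specified.

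**The concern.** The two endpoints share a model and a missing-data label but point in opposite directions. On the GES the counted event is good, so a non-responder is a patient without the good outcome, and the rule is conservative. On the hypoglycemia questionnaire the counted event is bad. A non-responder in the ordinary sense, a patient without the counted event, is then a patient without hypoglycemia, and silence is scored as the favourable result.

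That would sit badly with the rest of the SAP. A patient who leaves the study at month 3 with no recorded event and no month-6 questionnaire would be a failure on the 6-month composite (SAP 2.5.2). The same patient would have missing hypoglycemia status in the multiple-imputation analysis (SAP 2.4.4.1), yet be hypoglycemia-free on the questionnaire.

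At stake is a between-arm comparison of patient-reported hypoglycemia, which both documents name in the secondary objectives. The trial is open label and offers different support programs in the two arms (Protocol 8), so equal questionnaire return cannot be taken for granted.

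**Working it through.** The documents state no event rate, missing rate or power for this endpoint, so there is no plan figure to reproduce. The check has two parts: what the rule means, and what each meaning does to the result.

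**Direction of the rule**

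| | GES | Hypoglycemia questionnaire |
|---|---|---|
| Counted event | Complete control or marked improvement | At least one moderate or severe episode |
| Event is | Favourable | Unfavourable |
| Non-responder = lacks the counted event | Unfavourable result | Favourable result |
| Non-responder = failure | Unfavourable result | Hypoglycemia counted |

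For the GES the two meanings coincide. For the hypoglycemia questionnaire they are opposites, and the SAP does not choose between them.

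**Effect on the rates**

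Let p be the true rate and m the missing fraction in an arm. Missingness is taken as unrelated to the event. Both p and m are assumptions.

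- Coding A, missing = no hypoglycemia: p(1 − m)
- Coding B, missing = hypoglycemia: p(1 − m) + m
- Excluded: p

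Coding A lowers the rate by the relative fraction m, an absolute shortfall of pm. Coding B raises it by m(1 − p). The gap between the codings is always m.

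With the same p in both arms, the difference arm 1 − arm 2 is p(m2 − m1) under A and −(1 − p)(m2 − m1) under B. The signs are always opposite.

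*Main illustration:* p = 25% in both arms, m = 20% in arm 1 and 15% in arm 2.

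- A: 0.25 × 0.80 = 20.0%; 0.25 × 0.85 = 21.25%; difference −1.25 points.
- B: 20.0% + 20% = 40.0%; 21.25% + 15% = 36.25%; difference +3.75 points.
- Excluded: 25% in both arms; difference 0.

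With 1662 patients per arm (SAP 1.3.2) and an unadjusted z = difference / √(2p̄(1 − p̄)/1662):

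- A: p̄ = 0.20625, standard error 0.0140, z = −0.9.
- B: p̄ = 0.38125, standard error 0.0168, z = +2.2.

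*Range:* equal true rates, 15% missing in one arm and 25% in the other.

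| True rate | Coding A | Coding B |
|---|---|---|
| 5% | 4.25% v 3.75% (+0.5, z = 0.7) | 19.25% v 28.75% (−9.5, z = −6.4) |
| 20% | 17% v 15% (+2.0, z = 1.6) | 32% v 40% (−8.0, z = −4.8) |
| 30% | 25.5% v 22.5% (+3.0, z = 2.0) | 40.5% v 47.5% (−7.0, z = −4.1) |

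*Equal missingness:* with true rates of 15% v 20% and 20% missing in both arms, A gives 12% v 16% and B gives 32% v 36%. Both shrink the true difference of 5 points to 4.

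**Two further gaps**

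The rule speaks of items 4 *and* 5 being missing and does not say what happens when only one is. The items themselves also disagree: the Protocol synopsis and SAP 2.1.7.3 use items 4 and 5, while Protocol 9.3.1 uses 5 and 6. The questionnaire is not in the text available here, so the numbering cannot be checked.

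**The case against.** A reader might infer that the SAP has adopted a rule that scores missing data as the good outcome, by copying the GES rule without reversing it. The documents do not support that as a statement of fact. The term is undefined for this questionnaire. Standing beside the GES bullet, where it denotes the unfavourable result, it could equally mean failure, that is, hypoglycemia counted. SAP 2.5.2, which treats missing hypoglycemia information as failure on the composites, fits that meaning. Nothing shows how the sentence came to be drafted, or which arm will lose more questionnaires, so a bias in favour of Toujeo cannot be claimed either. This part of the objection stands.

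The rest of the SAP also gives some protection. Numbers missing are to be presented when relevant, and imputed cases identified where applicable (SAP 2.5.3). The questionnaire items are also summarised descriptively (SAP 2.4.7). Patients who stop treatment have assessments at that point and are asked to return (Protocol 6.2.1 and 10.3.3), and SAP 2.5.4 allows wide visit windows. Hypoglycemia is analysed mainly from e-CRF events (SAP 2.4.5.1), no alpha is allocated to this endpoint, and at smaller imbalances the distortion under coding A is modest.

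The general rule on missing categorical data permits stated exceptions, and the composite and imputation rules concern e-CRF events. The mismatch is therefore one of policy, not a formal contradiction.

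None of this supplies the missing definition. Two programmers could follow the sentence faithfully and produce opposite results, and no sensitivity analysis for this endpoint would reveal it.

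**Conclusion.** The point holds in this form: the rule assigns an undefined status to missing answers on an unfavourable endpoint. Its literal reading counts them as no hypoglycemia, and its main alternative counts them as hypoglycemia. Under the literal reading the rate is understated in proportion to the missing fraction and, with equal true rates, the arm with more missing data looks safer. That departs from how SAP 2.4.4.1, 2.5.2 and the general rule in 2.5.3 treat missing information. Under the alternative the rate is overstated and that arm looks worse.

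The arm rates under the two readings differ by the full missing fraction. In the main illustration the comparison moves from −1.25 to +3.75 points. The size rests on assumed event and missing rates and on missingness unrelated to the event. The change of sign needs equal true rates and unequal missingness; with equal missingness the two codings give the same, diluted difference.

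The consequence is confined to one patient-reported endpoint. The primary composite is not affected. The rule should be corrected before the 6-month database lock.

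**What to change.** Amend SAP 2.5.3 as follows.

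1. Delete the non-responder rule for the hypoglycemia questionnaire; keep it for the GES.
2. Define the endpoint value explicitly. Event: either item reports at least one episode. No event: both items are answered and neither reports an episode. Otherwise: missing, and excluded under the general rule for categorical data. Requiring both items to be answered before a patient counts at all would discard known events.
3. Add a sensitivity analysis that counts missing as hypoglycemia reported, or uses multiple imputation. The former should be read as a bound, since it is itself sensitive to unequal missingness.
4. Tabulate by arm and visit the number of patients with one item and with both items missing.
5. Reconcile the item numbers between the Protocol synopsis, Protocol 9.3.1 and SAP 2.1.7.3 against the questionnaire itself.

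The cost is a few lines of text, one extra analysis and one table. The complete-case main analysis assumes data are missing at random given the model's covariates. A patient with one item answered is kept if that item reports an episode and dropped if it does not, which pushes the rate up slightly; the table in step 4 shows how many patients this concerns.

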2.5.4 Windows for time points

The following process will be applied for Month 6, Month 12, premature EOT visits and unscheduled visits re-allocation. Re-allocated visits will be used in statistical analyses for the following endpoints: HbA1c, FPG, Body weight, dose and PROs (descriptive statistics, graphs, and statistical models).

Assessments will be re-allocated to the closest visit using the time windows given in [Table 7](#).

Table 7 - Re-allocation time windows definition

Re-allocated scheduled visit	Targeted study day/month	Re-allocation time windows in study days/month as 30-day period
Visit 3 (Month 6)	180 (Month 6)	(120-240)/end of Month 4 to end of Month 8
Visit 4 (Month 12)	360 (Month 12)	(300-420)/end of Month 10 to end of Month 14

Study days are calculated from the randomization day, being Day 1.

If more than one visits/measurements fall into a visit window, the one closest to the scheduled visit will be used.

For efficacy labs, only central lab data will be used.

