6.2 DURATION OF STUDY PARTICIPATION

6.2.1 Duration of study participation for each patient

During the planning phase of the trial, payer, research organization, and provider data bases will be reviewed to identify sites and patients eligible for the study.

After the data base review, the trial will consist of:

- 1 week screening period at site by clinician to screen the identified potential subjects
- 26 week treatment period for primary efficacy endpoint
- 26 week extension period for collecting persistence data and additional safety data.

The maximum study duration will be 53 weeks per patient.

For patients who prematurely discontinue the trial, the end of treatment visit assessments (Day 180 data) will be performed at the time of discontinuation at an EOT visit. In addition, an early end of trial (EOT) CRF page will be completed which includes the reason for stopping the treatment. Patients are then asked to return for their regularly schedule visits off treatment.

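### SAP 2.5.4 applies a closest-record rule to a questionnaire that asks about hypoglycemia since the last visit, so some reports made at an early end-of-treatment visit drop out of that endpoint

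*SAP*

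**What the plan says.** SAP 2.1.7.3 defines the HPQ endpoint from Questions 4 and 5 as a report of "one or more episodes of either moderate or severe hypoglycemia since the last visit", at 6 and 12 months. The same section also says: "This questionnaire will require them to report frequency of hypoglycemia experienced during the course of the study". (Protocol 9.3.1 names Questions 5 and 6; the synopsis and the SAP name 4 and 5.) SAP 2.4.7 compares the proportion between arms by logistic regression.

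On visits, Protocol 6.2.1 says that for early discontinuation "the end of treatment visit assessments (Day 180 data) will be performed at the time of discontinuation at an EOT visit". It adds: "Patients are then asked to return for their regularly schedule visits off treatment". Protocol 10.3.3 instead names the Day 360 assessments for the EOT visit. Both sets include the HPQ (Protocol 10.1.1.3 and 10.1.1.4).

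SAP 2.5.4 states: "The following process will be applied for Month 6, Month 12, premature EOT visits and unscheduled visits re-allocation". Its list of endpoints is "HbA1c, FPG, Body weight, dose and PROs", with no exception for recall items. Table 7 sets the windows at Days 120-240 for Month 6 and Days 300-420 for Month 12. Within a window, "If more than one visits/measurements fall into a visit window, the one closest to the scheduled visit will be used".

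**The concern.** Choosing the value nearest a target day suits a state measurement such as HbA1c or weight, where the later reading stands in for the earlier one. An answer about episodes since the last visit describes an interval. Two successive forms cover two different intervals, and keeping one loses the other. The SAP has no rule that combines HPQ answers within a period.

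The patients who produce two forms before Month 6 are mainly those who stopped IMP, the group in which lost reports are least likely to be a random subset. A patient who reported an episode at EOT could be analysed as having reported none. Elsewhere the SAP counts any event. In 2.4.4.1 the primary analysis uses hypoglycemia events whether or not IMP was stopped, and the imputation rules there count a patient with an event in the period as positive whether that patient completed or withdrew.

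**Working it through.** **Which form is used.** Let the EOT form fall on day *e* and Visit 3 on day *v*. An EOT form outside Days 120-240 is not available for Month 6. Inside the window it is used only if |*e* - 180| < |*v* - 180|. Visit 3 is allowed on Days 150-210 (Day 180 ± 30). For EOT days from Day 2 until Visit 3 (until Day 179 if Visit 3 is not attended):

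| Visit 3 | EOT days used | EOT days set aside by the closest rule | Tie, no rule | Outside the window |
|---|---|---|---|---|
| Day 150 | none | 120-149 | none | 2-119 |
| Day 165 | none | 120-164 | none | 2-119 |
| Day 180 | none | 120-179 | none | 2-119 |
| Day 195 | 166-194 | 120-164 | 165 | 2-119 |
| Day 210 | 151-209 | 120-149 | 150 | 2-119 |
| Not attended | 120-179 | none | none | 2-119 |

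Example: with Visit 3 on Day 195 the distance is 15. EOT on Day 166 (distance 14) is used and EOT on Day 164 (distance 16) is not. Where the EOT form wins, the Visit 3 form is set aside, so the interval after EOT is lost instead.

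**After Visit 3.** EOT on Days 241-299 (299 - 241 + 1 = 59 days) lies in neither window. EOT on Days 300-359 loses to a Visit 4 on Day 360, but is used if Visit 4 is missed.

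So there are two separate routes to loss: the closest-record sentence, and the Table 7 windows themselves.

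**Size, for illustration only.** The documents give no rates, so every input here is an assumption. Let *s* be the share of an arm who stop before Visit 3, complete both forms and have the EOT form set aside. Let *p* be the proportion of them positive at EOT, and *q* = 5% the proportion of those also positive at Visit 3. The understatement of the arm's Month 6 proportion is *s* × *p* × (1 - *q*).

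- Low: 0.10 × 0.20 × 0.95 = 1.9 points.
- High: 0.20 × 0.50 × 0.95 = 9.5 points.

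For the difference between arms, take *s* = 15% in arm A and 12% in arm B:

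- *p* = 40% in both: 0.95 × 0.40 × (0.15 - 0.12) = 1.1 points in favour of A.
- *p* = 50% in A, 30% in B: 0.95 × (0.15 × 0.50 - 0.12 × 0.30) = 3.7 points in favour of A.
- *p* = 30% in A, 50% in B: 0.95 × (0.15 × 0.30 - 0.12 × 0.50) = -1.4 points, now in favour of B.

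The sign depends on inputs that the documents do not supply.

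**The case against.** Several points on the other side stand.

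- **Recall period.** The questionnaire itself (Protocol Appendix H) is not in the text available for this review. SAP 2.1.7.3 mentions both the time since the last visit and the course of the study, and nothing says whether an EOT visit counts as the last visit. If patients recall back to the last scheduled visit, those who return lose little. An early EOT form from a patient who never returns would still go unused.
- **Second form.** Protocol 10.3.3 brings stoppers back at Day 180 for HbA1c and hypoglycemia review and does not mention questionnaires. Protocol 10.3.4, however, has them followed under the study procedures. If no second form is completed, an EOT form inside the window is used.
- **Reach.** A reader might infer that the SAP keeps one form per patient, or discards EOT forms as a class. It does neither: it keeps one record per window, and the table shows when an EOT form is used.
- **Who stops what.** A reader might infer that these patients have stopped insulin. They have stopped IMP; Protocol 10.3.5 has later insulin recorded as concomitant medication.
- **Other capture.** Stoppers are asked to keep reporting events in the e-diary (Protocol 10.3.3), and the primary and safety hypoglycemia analyses use recorded events (SAP 2.4.4.1 and 2.4.5.1).

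It can also be said that an any-positive rule changes the endpoint. That is weaker. For a patient with no EOT visit, the Visit 3 form looks back to Visit 2 (leaving standard-of-care visits aside), so counting both forms restores the same coverage for a stopper. What does stand is that two shorter recall periods are not identical to one longer one.

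**Conclusion.** The point holds in a limited form. Followed as written, SAP 2.5.4 can remove a positive EOT report when the patient returns for a Visit 3 closer to Day 180 and recall restarts at EOT. It always leaves unused an EOT form completed before Day 120 or on Days 241-299. The first route depends on the EOT visit counting as the last visit and on a second form being completed; the second route depends on neither.

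The effect is confined to one exploratory PRO comparison. A reader might go on to infer that the rule favours a particular arm, or reverses the meaning of the endpoint. The documents do not support this: they give no discontinuation or positivity rates by arm, and the illustration changes sign with the inputs. Losing positive reports understates the proportion and can count reporters as event-free; that is as far as the text goes.

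A related gap could add to the loss. SAP 2.5.3 makes patients with Questions 4 and 5 missing non-responders, which has no clear meaning for an adverse outcome. If it means no hypoglycemia, a patient whose only form was a positive one before Day 120 could be analysed as having had none. The point is worth correcting but does not threaten the trial's main conclusions.

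**What to change.** In SAP 2.5.4, exempt HPQ Questions 4 and 5 from the closest-record rule and define:

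- **Month 6:** positive if any HPQ completed after Visit 2 and up to Visit 3 (or up to Day 240 if Visit 3 is not attended) reports one or more moderate or severe episodes. A premature EOT form counts on whatever day it was completed.
- **Month 12:** the same, from after that cut-off up to Visit 4 (or Day 420 if Visit 4 is not attended).
- **Missing:** a patient with no positive form and no form in the Month 6 or Month 12 window is missing for that time point. SAP 2.5.3 should say whether non-responder means with or without hypoglycemia.

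Tying the cut-off to Visit 3 attendance avoids using the closest-record rule to define its own replacement. The item numbers should be confirmed against Appendix H, given the different numbering in Protocol 9.3.1.

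The cost is a short SAP paragraph and a derived variable from forms already collected. The small downside is that stoppers contribute two shorter recall periods and completers one longer one. The closest-record derivation now in the SAP can be kept as a sensitivity analysis to show whether that matters.
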